Title: Effect of Oral Calcium Carbonate on Uterine Contractility

and Labor Outcomes: A Randomized Controlled Trial

Short Title RCT: Oral Calcium Supplementation in Labor

NCT Number: pending Protocol Date: 4-26-24

Principal Investigators

[name], DO [name] [name] [name], DO, MPH, MFM [name], MFM, MBA

Arrowhead Regional Medical Center Department of Women's Health [name] Work: [contact]/ [contact]

email: [contact]

II: Introduction/Literature review:

In the United States, cesarean delivery rates affect one in three women, with labor dystocia frequently cited as a leading cause. Labor dystocia can arise from various factors such as fetal size, positioning, pelvic structure, contractions, or maternal conditions. Clinically we can only correct the amount of uterine activity by oxytocin administration \pm amniotomy. The inability to decrease the cesarean section rate has prompted exploration for additional strategies.

One proposed method to improve uterine activity that has sparked interest in numerous social group forums is oral calcium carbonate supplementation, yet it remains largely unstudied in a clinical setting. Both calcium and carbonate components are recognized for enhancing myometrial contractility.² Physiologically, calcium plays a vital role in regulating uterine contractility throughout pregnancy.² Oxytocin triggers the release of calcium ions from intracellular stores via L-type Calcium channels within myometrial cells, inducing action potentials and thereby uterine contractility.³ During labor, there's an upsurge in calcium channel expression, facilitating uterine contractility.³ Additionally, serum calcium levels have been correlated with uterine contractility, as patients with higher calcium levels are more likely to deliver vaginally compared to those undergoing cesarean delivery.² ⁴⁻⁶

Given its potential to enhance uterine contractility and potentially reduce the need for surgical intervention, we aim to investigate the effects of calcium carbonate on uterine contractility. We hypothesized that giving calcium carbonate intrapartum can improve uterine contractility and decrease the number of cesarean deliveries.

III: Objectives: research question, purpose of the study, hypothesis

- Research questions:
 - Does calcium carbonate supplementation intrapartum improve uterine contractility, assessed by measuring Montevideo units, contraction frequency, and peak contraction strength.
- Purpose of the Study: The purpose of the study is to investigate whether calcium carbonate supplementation during labor can improve uterine contractility and decrease labor dystocia. By conducting this trial, the aim is to provide evidencebased guidance to healthcare providers regarding the potential use of calcium carbonate as a preventive measure for labor dystocia.
- Hypothesis: We hypothesized that pregnant women, those who receive calcium carbonate supplementation will have improve uterine contractility and a shorter labor course.
- Alternative Hypothesis: Calcium supplementation will have no effect on contractility

IV: Study type: Randomized control trial

V: Methods:

Location: Labor and Delivery at Arrowhead Regional Medical Center

- Start: Plan to start at the receipt of IRB approval. We anticipate the duration of the study to be about 2 years.
- Type of research: other
- Inclusion:
- Patients undergoing induction of labor with an intrauterine pressure catheter already in place at the discretion of the OB provider
- Maternal age: >18 years of age
- Gestational age > 37 weeks 0 day
- Cephalic presentation
- Able to understand/read English and/or Spanish
- Exclusion:
 - Maternal age < 18 years of age
 - Incarcerated patients
 - Active labor
 - Active illicit substance use
 - Multiple fetal gestations
 - Bleeding concerning for hemorrhage/placental abruption/placenta previa, or other contraindications to vaginal delivery
 - Aneuploidy or fetal structural anomaly
 - Prior cesarean deliveries
 - Known maternal arrhythmias, hyperparathyroidism, heart failure, kidney failure, liver failure, and history of kidney stones
 - Medications that affect uterine contractility like Magnesium, Terbutaline, Cytotec (need to be 4 hours after administration to enroll)
- Subject recruitment: All women with a term pregnancy, admitted for induction of labor will be asked to participate if age >18 years of age and English/Spanish speaking. We will plan to recruit when a patient is at least 4 cm and greater with an IUPC already in place. Using a baseline Montevideo unit of 200, if we were to aim for a 20% difference with a power of 80%, a sample size of 80 would be the minimum goal to enroll. Therefore, our goal is to enroll at least 40 patients into each group.

Consent:

- The informed consent process will be conducted by trained research staff and will include all aspects of the study and a full disclosure of the risks, benefits, procedures, and alternatives. The study consent and HIPAA authorization will be signed after all questions have been discussed and answered. Collection of baseline information, including such items as contact information, BP measurements, demographic and pregnancy history information, concomitant medications, and lifestyle information will follow the informed consent process.
- All data will be kept confidential to comply with HIPAA regulations. No
 patient identifiers will be included in the data sets. All data will be kept in a
 password protected folder within the ARMC network and will only be made

- available to study investigators. The database will be controlled, and password-protected.
- All data and records will be kept confidential in accordance with Institutional policies and HIPAA. There will be extremely limited access to subject information. All data will be anonymized before publication. Patient Data Sets will include identifiers that are strictly limited to medical record number, ethnicity, age and sex, along with associated clinical data. Patient Data Sets will be imported into password protected Excel files located in an encrypted folder accessible only to the investigators involved in the study, IRB, and IT on the ARMC server. All published poster presentations, abstracts and papers will be de-identified, with a medical record numbers and any other identifying material removed. Patient's age, parity, sex and race will be used in publication for educational purposes.

VI: Study Design and analysis:

- All patients admitted for term induction of labor will be asked to participate if they
 meet the inclusion criteria as described above. Once consented, the participants
 will be randomly allocated into two groups: control versus intervention group.
 Randomization will be done as block randomization based on maternal BMI at
 time of admission, all odd patients will be enrolled into the control group and all
 even study numbers will be in the intervention group.
 - -Control group: no medication
 - -Intervention group: Calcium carbonate 500 mg 4 tablets PO x1 -Calcium carbonate (TUMS) is an over-the-counter antacid medication and common side effects include changes in bowel habits like constipation or diarrhea, bloating, gas, and abdominal discomfort. Rare side effects include allergic reactions and hypercalcemia if taken in large amounts. The daily recommended max dose is 8000mg, we will be giving a max of 2000 mg.⁷
- The primary outcome will determine the effect of calcium carbonate on uterine contraction strength, assessed by comparing Montevideo units (MVU), frequency of contractions, and peak of the contractions 30 minutes before medication administration and at 30 minutes interval for a total of 2 hours afterward. To ensure accuracy in MVU measurement, all patients should already have an intrauterine pressure catheter (IUPC) in place at the discretion of the OB provider before they are enrolled. Secondary outcomes include duration of first and second stage of labor, mode of delivery, neonatal outcomes (NICU admission, low APGAR scores), and maternal outcomes (PPH).
- Other maternal information such as height, weight, BMI, age, parity, race, gestational age, cervical dilation/effacement/station at the time of medication administration and after administration, time to delivery, oxytocin use, epidural use, Apgars, perineal laceration, QBL, birthweight, mode of delivery, delivery complications will be obtained to compare among the two groups to make sure there are no confounding factors. Since Pitocin dose is a confounding variable after receiving the medication, patients must be off Pitocin during study period.

- The data collected will be divided into 2 groups: control versus intervention group. Statistical analysis included descriptive statistics to summarize maternal characteristics and clinical outcomes. Normality testing was performed, and appropriate comparative statistical tests were selected, including two-way Student's t-tests, Tukey's tests, or post hoc Student–Newman–Keuls tests as appropriate. A p-value of less than 0.05 was considered statistically significant. Univariate and multivariate linear regression analyses were conducted to identify associations between maternal, fetal, and labor-related variables and study outcomes.
- Uni- and multivariate analysis with linear regression modeling will be used to identify significant associations between maternal, fetal, or labor characteristics.

VII: Risks and Benefits:

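### The plan does not clearly require time off oxytocin before the 30-minute MVU baseline; fading oxytocin could add noise, which baseline adjustment and a last-oxytocin record would cheaply reduce

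*Combined protocol and SAP*

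**What the plan says.** Two rules in the combined protocol and SAP bear on oxytocin before the baseline.

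- Section V: Methods, Exclusion: "Medications that affect uterine contractility like Magnesium, Terbutaline, Cytotec (need to be 4 hours after administration to enroll". Three drugs are given as examples, and oxytocin is not one of them.
- Section VI: Study Design and analysis: "Since Pitocin dose is a confounding variable after receiving the medication, patients must be off Pitocin during study period". The plan states no start, no end and no minimum time off Pitocin.

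The primary outcome in section VI covers MVU, contraction frequency and "peak of the contractions 30 minutes before medication administration and at 30 minutes interval for a total of 2 hours afterward". The pre-dose reading is therefore part of the primary outcome.

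The participants are "Patients undergoing induction of labor with an intrauterine pressure catheter already in place at the discretion of the OB provider" (section V, Inclusion). Section II says of oxytocin: "Clinically we can only correct the amount of uterine activity by oxytocin administration", with or without amniotomy.

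Two collected items touch on oxytocin exposure. Section V, Consent, lists "demographic and pregnancy history information, concomitant medications, and lifestyle information will follow the informed consent process", and section VI lists "time to delivery, oxytocin use, epidural use, Apgars, perineal laceration, QBL, birthweight, mode of delivery, delivery complications will be obtained". Neither says that the time or rate of the last oxytocin is recorded.

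On analysis, section VI says "The data collected will be divided into 2 groups: control versus intervention group". It names t-tests and multiple-comparison tests, and adds linear regression to look for associations. It does not say whether the MVU comparison uses change scores, baseline adjustment or post-dose readings alone.

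**The concern.** The women are being induced, so oxytocin shortly before enrolment is plausible, although the documents do not say how common it is. If Pitocin is stopped just before the baseline window, the baseline may still carry its effect while the later readings do not. Women who were recently on oxytocin would then tend to show a falling MVU for a reason unrelated to calcium, and women who were not would show no such fall. That mixture widens the spread of change from baseline in both arms.

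What is at stake is precision in a trial of 40 per arm. The plan itself treats Pitocin as a confounder, but its stated reason concerns the time after dosing, and it says nothing explicit about the time before the baseline. The point here is oxytocin given before the baseline. Oxytocin restarted afterwards is a different matter.

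**Working it through.** **1. Do the two rules close the gap?**

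- *The 4-hour rule covers oxytocin.* The list is introduced as examples, and section II describes oxytocin as acting on uterine activity. On this reading there is no gap.
- *The 4-hour rule does not cover oxytocin.* Section VI gives Pitocin its own rule and does not refer back to a 4-hour interval. On this reading only the section VI rule applies. Even if the study period is taken to start with the baseline, which is its natural sense, nothing is required before that start, so stopping Pitocin just before the baseline complies.

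Both readings are fair, and two sites of practice within the unit could each comply while doing different things.

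**2. The plan's sample size.** Inputs from section V: baseline 200 MVU, 20% difference, 80% power, 40 per arm. Section VI gives a 0.05 threshold; two-sided testing is assumed. The target difference is 0.20 × 200 = 40 MVU. No SD is stated, so the total of 80 cannot be reproduced forwards and the SD has to be solved for:

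- Normal approximation: SD = 40 × √(40/2) / (1.95996 + 0.84162) = 63.85 MVU.
- Noncentral t with 78 degrees of freedom: SD = 63.06 MVU. This value is used below.

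**3. Noise from fading oxytocin (illustration).** Assume that 63.06 is the SD of the change score without this noise. Assume also that a share p of women in each arm have oxytocin fading at baseline, and that this lowers their later MVU by D. Both p and D are assumptions; the documents give neither.

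Added variance = p(1 − p)D². New SD = √(63.06² + added variance). Power is for 40 per arm and a 40 MVU difference.

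| p | D (MVU) | Added variance | SD | Power |
|---|---|---|---|---|
| 10% | 20 / 40 / 60 | 36 / 144 / 324 | 63.35 / 64.19 / 65.58 | 79.7% / 78.6% / 76.9% |
| 25% | 20 / 40 / 60 | 75 / 300 / 675 | 63.65 / 65.40 / 68.20 | 79.3% / 77.1% / 73.6% |
| 50% | 20 / 40 / 60 | 100 / 400 / 900 | 63.85 / 66.16 / 69.83 | 79.0% / 76.1% / 71.6% |

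p = 50% is the worst case, because p(1 − p) is largest there.

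**4. How far this depends on what 63 means.** If 63.06 is instead the SD of a single reading, and r is the before-after correlation, the change-score SD is 63.06 × √(2(1 − r)). It equals 63.06 only at r = 0.5. At r = 0.7 it is 48.8: power starts at about 95%, and the worst case above gives about 87%. At r = 0.3 it is 74.6, and power is about 66% before any oxytocin effect.

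**5. What baseline adjustment gains.** Take 63.06 as the SD of a single reading and r = 0.5, with no oxytocin noise. An unadjusted t-test on either the post-dose reading or the change has 80% power. Adjusting for baseline gives a residual SD of 63.06 × √(1 − 0.5²) = 54.61 and power of about 90%.

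**The case against.** The strongest reply is that the plan already deals with oxytocin. The 4-hour list is illustrative, Pitocin must be off during the study period, oxytocin use is collected, and regression on labor-related variables is planned. The control arm also absorbs any decline that both arms share. Much of this stands. The gap exists on only one of two fair readings, and what remains is a modest loss of precision built on assumed inputs. That loss disappears if the primary analysis uses later post-dose readings alone, or if the SD behind the 80 already includes this variation.

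The reply does not remove the ambiguity. Nor does a general record of oxytocin use supply the time since the last dose, which an analysis would need.

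Two stronger readings are tempting, and the documents support neither.

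- A reader might infer that fading oxytocin biases the calcium effect. A rule applied alike to both arms before allocation does not shift the between-arm contrast in expectation. Bias would need oxytocin to be stopped differently by arm. Allocation by odd and even study number might make that possible, but it is a separate issue, and nothing in the plan says that oxytocin is handled differently.
- A reader might infer that the before-after change within the calcium arm will understate a true rise. That would matter only for a within-arm test, and the plan specifies none.

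**Conclusion.** The point holds as a cheap improvement. The plan does not clearly require an oxytocin-free interval before the baseline, and the consequence is possible noise in the pre-dose MVU and in change from it. The size is unknown from the documents. Under the assumed shares and declines, the cost to a change-score analysis runs from under one percentage point of power to about eight (80% to 71.6%). Those figures require a change-score SD of 63 MVU and two-sided testing at 5%, and they are upper bounds if the planning SD already reflects mixed oxytocin exposure.

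The firmer gain is from the analysis. Using the baseline MVU that the trial already collects as a covariate raises power from 80% to about 90%, if the single-reading SD is 63 MVU and the before-after correlation is 0.5.

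**What to change.** 1. Make the primary MVU analysis a between-arm comparison adjusted for the 30-minute baseline MVU, in place of unadjusted t-tests.
2. Before allocation, record the time and rate of the last oxytocin, alongside the baseline items already collected after consent. Include one pre-specified term for recent oxytocin in the model, for example last oxytocin within 4 hours of baseline versus none or longer ago. The cut is for the sponsor to choose.
3. Define the study period as the start of the 30-minute baseline through 2 hours after dosing, or after a matched time zero in controls, who receive no dose. In the same place, say whether the 4-hour rule covers oxytocin.

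The cost is two recorded items, one or two model terms and a short clarification of the text. No extra patients or visits are needed.

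A mandatory oxytocin-free interval before baseline would remove the problem at source, but it would make some women eligible later or not at all. The documents do not say how many, so this is a recruitment trade-off for the sponsor and is not required.

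### The active-labor exclusion is undefined and collides with a recruitment rule that runs from 4 cm upward without limit, so the eligible population is not determined

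*Combined protocol and SAP*

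**What the plan says.** Three places in the combined protocol and SAP bear on this.

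- **Section V, Inclusion and Exclusion.** The population is "Patients undergoing induction of labor with an intrauterine pressure catheter already in place at the discretion of the OB provider". The inclusion list gives no dilation. The exclusion list has active labor as a bare two-word entry, with no criterion for recognizing it, no mention of how labor began and no time at which it is judged.
- **Section V, Subject recruitment.** Women admitted for induction are to be approached, and then: "We will plan to recruit when a patient is at least 4 cm and greater with an IUPC already in place". This is the only dilation rule in the plan, and it has no upper limit.
- **Section VI, Study Design and analysis.** Eligibility is restated only by reference back to the inclusion criteria. Neither active labor nor dilation is mentioned there as a condition of entry. The allocation text begins "Randomization will be done as block randomization based on maternal BMI at" admission, then says "all odd patients will be enrolled into the control group and all" "even study numbers will be in the intervention group". The comparator is "Control group: no medication". Among the variables to be collected is "cervical dilation/effacement/station at the time of medication administration and after administration", for comparing the groups.

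**The concern.** A woman whose labor has been induced and has advanced well past 4 cm satisfies the recruitment rule. On an ordinary reading of the words she may also be in active labor, and so excluded. The plan does not say which rule prevails.

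The first consequence is for who is studied. If screeners read the exclusion differently, the enrolled women will vary by screener, and the published eligibility criteria will not describe them.

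The second is for the comparison itself. An undefined exclusion gives a recordable reason to turn a woman away. In an open-label trial whose assignment may be foreseeable, such a reason deserves to be removed. Dilation plausibly relates both to contraction strength and to how soon a woman delivers within the 2-hour measurement period, so an imbalance in it would matter for the primary outcome.

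**Working it through.** The point is textual. The only number in the disputed rules is 4 cm. The planned sample size of 80 is not in question here and does not depend on how the conflict is resolved.

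**Step 1: write the two rules side by side.** Let d be cervical dilation when the woman is considered for recruitment.

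- Recruitment rule: d ≥ 4 cm, catheter in place, no upper bound.
- Exclusion rule: not in active labor, with the definition and the time of assessment both left open.

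**Step 2: work out who is eligible under each reading.** T is an unspecified dilation at which active labor would be taken to begin. The documents give no T, and none is proposed here.

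| Reading of the exclusion | Eligible women | Do the rules collide? |
|---|---|---|
| Judged at recruitment, T at or below 4 cm | None | Yes, for every woman |
| Judged at recruitment, T above 4 cm | 4 cm ≤ d < T | Yes, for women with d ≥ T |
| Judged at recruitment by something other than dilation | Cannot be stated from the text | Yes, for any woman at 4 cm or more who meets that criterion |
| Spontaneous labor at admission only | All with d ≥ 4 cm | No |

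Only the last row is free of conflict, and it needs two qualifiers, the type of onset and the time of assessment, that the plan does not contain. The second row needs an upper bound that the plan lacks and that its open-ended wording contradicts.

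**Step 3: look for a reconciling passage.** Section VI points back to the inclusion list, which is silent on both dilation and active labor. Its list of collected variables uses dilation descriptively and sets no cap. Section V describes an approach to women admitted for induction and a later recruitment point at 4 cm or more. It therefore contains two moments at which the exclusion might be applied, and does not choose between them.

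**Step 4: ask whether the arm could be known when the judgment is made.** Section VI assigns by the parity of the study number and describes no concealment. If numbers are issued in sequence, the next assignment can be foreseen. The plan does not say how numbers are issued, by whom, or whether recruiting staff see them. The same sentence also speaks of blocks based on BMI, without explaining how that fits with odd and even numbers. Foreknowledge is therefore possible but not established.

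**Step 5: check whether dilation can serve as a baseline covariate as collected.** It is to be recorded at the time of medication and afterward. Controls receive no medication, so the plan gives them no corresponding time. A comparable baseline value needs a time zero defined for both arms.

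**The case against.** The strongest reply is that the exclusion has a natural meaning. This is a trial in women admitted for induction, and a woman already in labor on arrival is not a candidate for induction. Read that way, the exclusion operates at admission, the dilation rule operates later, and nothing conflicts. This reading is plausible and may well be what was intended. It is the reason to treat the matter as a wording conflict to be repaired rather than a failure of the design. It does not remove the point, because the plan states neither qualifier and a screener applying the criteria at recruitment has no basis for supplying them.

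It can also be said that selection by arm would come mainly from predictable allocation. With concealment, this ambiguity would affect only who is represented. Without it, repairing this wording leaves other routes open, such as the consent approach and the provider's discretion over the catheter. That stands. Section VI also already places consent before allocation and plans multivariable regression, which partly covers the remedy. However, it does not require eligibility to be recorded before the number is issued, and it does not name dilation as a covariate in the treatment comparison.

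A reader might infer three stronger things, none of which the documents support:

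- **That no woman is eligible.** This requires active labor to begin at or below 4 cm, and no passage says so.
- **That staff will know the next arm and select on it.** The plan is silent on who issues numbers and when.
- **That the bias has a particular size.** There is no MVU standard deviation and no dilation distribution to work from. Even the direction is uncertain: if greater dilation goes with stronger contractions, this ground would tend to remove women with high MVU rather than low.

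**Conclusion.** The concern holds as a conflict between two stated entry rules. Under every reading except spontaneous labor at admission, at least some women at 4 cm or more are both recruitable and excluded, and nothing in the plan settles which rule applies. For the second row of the table, this assumes that T is a dilation some induced women reach before enrollment.

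The certain consequence is an undetermined eligible population and the possibility of inconsistent screening. Selection by arm is a conditional consequence: it requires study numbers issued in sequence and visible to those judging eligibility, and its root is the allocation method, which needs its own correction. No numerical size can be given. The change should be made before enrollment because it is cheap and because the population cannot be reconstructed cleanly afterward.

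**What to change.** 1. Reconcile the Exclusion list and the Subject recruitment paragraph in Section V into one entry rule, used in both places and in Section VI. It should state what active labor means in this trial, when it is assessed and what dilation range is intended. The clinical content is for the investigators to decide.
2. Require the cervical examination and the eligibility decision to be recorded before the study number is assigned, and log every woman excluded on this ground.
3. Define a common time zero for both arms: the medication time in the intervention arm and the matching time in controls. Record dilation at that point and name it as a prespecified baseline covariate in the treatment-effect model for MVU.
4. Deal with the odd/even allocation and its concealment separately. Steps 1 to 3 do not repair it.

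The cost is a wording change, a line on the screening log and a defined recording time for controls, for a measurement the plan already intends to collect. Depending on the rule chosen, a few fewer women may be eligible and accrual may be slightly slower.

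### Allocation is triggered by consent in an open trial, so the 30-minute primary-outcome baseline and the off-Pitocin condition can fall after the arm is known

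*Combined protocol and SAP*

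**What the plan says.** **Order of steps.** Section VI (Study Design and analysis) applies the inclusion criteria when a woman is asked to take part, and then moves straight from consent to assignment: "Once consented, the participants" "will be randomly allocated into two groups: control versus intervention group". No baseline recording or eligibility re-check is named between the two.

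**Arms.** The comparator is stated as "Control group: no medication". No placebo or blinding is described. The arm follows the study number within BMI blocks, with BMI taken at "time of admission, all odd patients will be enrolled into the control group and all" even numbers to the intervention.

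**Primary outcome.** Montevideo units (MVU), contraction frequency and peak are compared over this window: "peak of the contractions 30 minutes before medication administration and at 30 minutes interval for a total of 2 hours afterward". The baseline is thus anchored to dosing, not to enrolment or allocation. The same section requires the pressure catheter to be in place before enrolment, but sets no minimum length of tracing.

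**Recruitment.** Section V, Subject recruitment, has two statements. The first is "All women with a term pregnancy, admitted for induction of labor will be asked to participate if age >18 years of age and English/Spanish speaking". The second is "We will plan to recruit when a patient is at least 4 cm and greater with an IUPC already in place".

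**Conditions around enrolment.** The 4-hour washout in the Section V exclusion list is tied to enrolment. The requirement to be off Pitocin is in Section VI and covers a study period whose start is not given.

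**The concern.** The before/after comparison rests on the baseline. Once the arm is known to the woman and the staff, that knowledge can affect the conditions under which the baseline is recorded, the stretch of tracing used, and whether a woman is judged to meet the off-Pitocin condition. A distortion of the recorded baseline in one arm passes in full into a difference in change from baseline. Controls add a further difficulty: they receive no medication, so someone has to choose where their 30 minutes end.

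Women may also leave between allocation and dose, or before the 2 hours of monitoring are complete. The plan does not say how they are analysed and gives no allowance for loss. If they are left out, the comparison is no longer between the groups as allocated. With 40 per arm, each woman is 1/40 = 2.5% of her arm.

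**Working it through.** **1. Where the baseline falls.** Let c be the minutes of catheter tracing available before allocation, and g the minutes from allocation to time zero (dosing, or whatever stands in for it in controls). The baseline is the 30 minutes that end at time zero.

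- The part recorded after allocation is the smaller of g and 30.
- A complete baseline needs c + g of at least 30, so at least 30 − c minutes follow allocation whenever c is below 30.
- Assumed c = 0: all 30 minutes follow allocation. Assumed c = 10: at least 20 of 30. Assumed c = 20: at least 10 of 30.
- With c of 30 or more, the baseline precedes allocation entirely only if g = 0.

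The plan gives neither a minimum for c nor any value for g. For controls, g has no defined end point.

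**2. Which conditions are settled before allocation.** The catheter requirement (inclusion list and Section VI), the 4 cm condition (Subject recruitment) and the 4-hour washout (exclusion list) all attach to recruitment or enrolment. The off-Pitocin condition attaches to the study period, so it can be judged, or can fail, after allocation.

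**3. The plan's sample size.** Inputs from Subject recruitment are a baseline of 200 MVU, a 20% difference (0.20 × 200 = 40 MVU), 80% power and 40 per group. The 0.05 level comes from Section VI; two-sided testing is assumed. No SD is given, so 80 cannot be reproduced directly. Solving for the SD:

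40 / [(1.960 + 0.842) × √(2/40)] = about 63.9 MVU.

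An SD of 63.8 returns 40 per group and 80 in total.

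**4. What loss after allocation would do.** The loss rates are assumptions. Power is Φ[δ / (63.8 × √(2/n)) − 1.960].

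Lost from both arms and left out (δ = 40):

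- 5%: n = 38, power 78.0%
- 10%: n = 36, power 75.8%
- 15%: n = 34, power 73.4%
- 20%: n = 32, power 70.8%

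Keeping 40 per arm after such losses needs 40/(1 − loss), rounded up: 86, 90, 96 and 100 women in total.

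If instead all 40 per arm are kept as allocated, and undosed intervention women gain nothing, the difference is diluted. At 10% undosed δ = 36 and power is 71.3%; at 20% δ = 32 and power is 61.1%. Analysing as allocated protects the comparison but does not restore power, which is a further reason to move allocation later.

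**The case against.** The strongest reply is that this is silence and not a stated flaw. A reader might infer that the plan takes the baseline only after allocation. It does not say so. The catheter is in place before enrolment, so for many women the 30 minutes could come from tracing already on record. That is right, and the point is limited accordingly: the plan permits a post-allocation baseline, and forces one only when the catheter has been in for less than 30 minutes.

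A reader might also infer that women consented at admission will be allocated and then never reach 4 cm or never receive a catheter. The documents do not support this as the plan's intention. Section VI ties the approach to the inclusion criteria, the catheter is one of them, and Subject recruitment sets 4 cm with a catheter as the recruitment point. The two recruitment sentences can be read as who is approached and when they are enrolled. The wording is loose and should be reconciled, but that scenario depends on misreading it.

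A third temptation is to put a size on selective loss. If 4 of 40 intervention women, each assumed to be 60 MVU below the mean, were not dosed, the arm's mean baseline would rise by 4 × 60/36 = 6.7 MVU, or 17% of 40. With 8 lost it would rise by 8 × 60/32 = 15 MVU, or 38%. The number lost, the one-sided loss and the 60 MVU are all assumptions. The results are shifts in baseline and do not carry one-for-one into a change-based or baseline-adjusted comparison. They are not estimates of bias in the effect.

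Finally, reordering alone does not stop staff foreseeing the arm from odd/even numbers. That stands. Equally, a concealed list alone would leave open arms with a baseline that can follow allocation.

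**Conclusion.** The concern holds in a limited form. Allocation on consent, open arms, a baseline anchored to dosing, no required tracing beforehand and no time zero for controls together leave the primary-outcome baseline and the off-Pitocin condition open to knowledge of the arm. Women allocated but not dosed or not monitored have no analysis rule.

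The only firm quantity is the timing result: a woman with c minutes of prior tracing, c below 30, has at least 30 − c baseline minutes after allocation. How many women this affects, and how far it would move the estimate, cannot be derived from the documents. The power figures rest on the implied SD of about 63.8 MVU, two-sided testing at 0.05 and assumed losses. The change is worth making because it replaces the stated allocation point with a less bias-prone one at little cost.

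**What to change.** - In Section VI, replace consent as the trigger for allocation. Participants should be allocated only after consent, after confirmation that every existing eligibility condition is met (including catheter in place, 4 cm or more, washout and off Pitocin), and after a complete 30-minute baseline tracing has been closed.
- Use the time of allocation as time zero in both arms. Define the baseline and the four 30-minute follow-up intervals from it, and revise the primary-outcome definition to match. This sets the measurement clock and prescribes nothing about dose timing.
- State that every allocated woman is analysed in her assigned arm, including those not dosed or not monitored for the full 2 hours.
- Reconcile the two sentences under Subject recruitment, and define when the study period for the off-Pitocin condition starts and ends.
- Replace odd/even numbering with a concealed random list. Without this, the reordering gives only partial protection.

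**Cost.** The sequence change is an edit to the text. It makes a completed tracing a condition of allocation. Some consented women will never be allocated and must be logged as screen failures, so more than 80 may need to consent to reach 80 allocated. The concealed list needs a separate, modest arrangement.
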